**Table 4-1: Visit windows for KCCQ**

Analysis time point	Scheduled visit date	Scheduled visit window
Baseline	Day 1	Day 1
Week 2	Day 14	Day 2 – Day 27
Week 6	Day 42	Day 28 – Day 62
Week 12	Day 84	Day 63 – Day 104
Week 18	Day 126	Day 105 – Day 146
Week 24	Day 168	Day 147 – Day 181
Safety follow-up*	Day 196	Day 182 – Day 209

\*If patients have completed all scheduled doses. In case of premature discontinuation, safety follow-up will be scheduled at  $28 \pm 7$  days after the last dose, and the visit window will span from two weeks before the scheduled safety follow-up visit to two weeks after.

## 4.2 Handling of Missing Data

All missing or partial data will be presented in the subject data listings as they are recorded on the electronic Case Report Form (eCRF) or electronic PRO diary (ePRO).

For missing components in KCCQ domains, the algorithm for score calculation will follow the KCCQ scoring instructions [10]. For example in the PLS domain, if a patient answers “Limited for other reasons or did not do the activity”, the response will be considered as missing. KCCQ scoring instructions specify that at least 3 out of 6 non-missing components are needed for the domain to be evaluable.

Non-evaluable domains will be treated the same way as missing domains and will be handled based on missing data imputation rules specified in Appendix 9.1.

## 4.3 Interim Analyses and Data Monitoring

An independent Data Safety Monitoring Committee (DSMC) has been established for this study. The DSMC will review safety and tolerability regularly, and conduct the futility interim analysis during the course of the study. Members of the DSMC will receive unblinded safety data. The involvement of an external Statistical Analysis Center in this process will ensure that unblinded information is not available to anyone except the DSMC. The study team and study committees (steering committee and the PRO sub-committee, see below) will be kept blinded in this process. There are no predefined stopping conditions for the ongoing safety monitoring of this trial. However, the DSMC may recommend termination, temporary suspension of the study, and intervention of treatment arm or modification of the study. Details on DSMC responsibilities and decisions, as well as a detailed plan for DSMC meetings will be described in the DSMC Charter.

A sub-committee of the study steering committee will be focused on PROs (called PRO sub-committee). The PRO sub-committee is made up of an additional panel of experts in the field acting in support of the steering committee. Steering committee and PRO sub-committee will review and monitor the blinded PRO data regularly to ensure data quality and completeness. The PRO sub-committee will also contribute to the interpretation of the analyses to evaluate important within patient change which will be used to determine the responder definitions for

the KCCQ-PLS. Details on PRO sub-committee membership, roles, responsibilities and operational aspects will be described in the PRO sub-committee charter.

#### 4.3.1 Futility interim analysis

A single interim assessment by the DSMC to evaluate futility is planned for when 50% of the patients complete Visit 7 (week 12) and their KCCQ data become available. Although the effects of 24 weeks of treatment with vericiguat have not been evaluated in patients with HFpEF, prior data in this population suggest that the 12 week timepoint will be sufficiently predictive of the 24 week data to allow for an adequate interim assessment of efficacy. Furthermore, in view of the expected timeline for patient recruitment, a sufficiently large proportion of data at the 24 week timepoint will only become available shortly before completion of the trial. Based on the operating characteristics of a range of futility criteria (Table 4-2), an observed mean treatment effect of 0.6 point difference in KCCQ PLS (vericiguat vs placebo) was chosen to serve as the boundary for futility for both dose groups; this is approximately equivalent to a joint conditional power (CP) of 23% at week 24 (under the assumption of a true difference of 5 points and a SD of 21 points).

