22 FEB 2018

Version no. 1.0

Page: 9 of 81

the boundary for futility for both dose groups, which is approximately equivalent to a joint conditional power (CP) of 23%. An observed difference <0.6 in both comparisons would therefore signal to the DMC that the trial should be terminated early. At this futility boundary the trial has a joint probability of 9% to observe a >5 point improvement in either of the dose groups.

In addition, a blinded anchor-based interim analysis will be conducted upon the completion of the 3-month assessments by all trial participants. A non-parametric discriminant analysis will be used to determine the discrimination point between “no change” and “a little better” categories, which is considered to be Minimal clinically important difference (MCID).

Based on the blinded anchor-based interim analysis, the percentages of responders with MCID, moderate, and large differences at each visit will be summarized, and nominal p-values will be also provided.

The study uses the graphical method of Maurer and Bretz (2013) to provide strong multiplicity control across the primary KCCQ PLS hypotheses and the secondary 6 MWT hypotheses. The overall two sided alpha level will be controlled at 0.05. The two primary hypotheses will be tested using Bonferroni procedure, each at a splitted alpha of 0.025. The two secondary hypotheses will be tested based on parallel gatekeeping principle. If both primary hypotheses can be rejected, the secondary family will be tested at a full alpha level 0.05 (two sided). If only one primary hypothesis has shown to be statistically significant, then only the secondary hypothesis based on the same dose group can be tested at an alpha level carried forward from the primary family testing, i.e., 0.025 (two sided). In this case, if the secondary hypothesis is rejected, the alpha spending associated with this dose group (0.025) will be re-utilized to test the other failed primary hypothesis again. Overall, the primary analysis will be claimed to have a positive outcome if the null hypothesis for at least one of the two primary hypotheses can be rejected.

Table of contents

1. Title page.....	1
Signature of the sponsor's medically responsible person	2
Signature of principal investigator	3
2. Synopsis.....	4
Table of tables.....	12
Table of figures	12
List of abbreviations.....	13
3. Introduction.....	16
3.1 Background	16
3.2 Previous experience in humans.....	17
3.2.1 Dose selection.....	18

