10.5 Planned interim analyses

Futility interim analysis

A single interim assessment by the DMC to evaluate futility is planned for when 50% of the patients complete Visit 7 (week 12) and their KCCQ data become available. Although the effects of 24 weeks of treatment with vericiguat have not been evaluated in patients with HFpEF, prior data in this population suggest that the 12 week timepoint will be sufficiently predictive of the 24 week data to allow for an adequate interim assessment of efficacy. Furthermore, in view of the expected timeline for trial conduct, a sufficiently large proportion of data at the 24 week timepoint will only become available shortly before completion of the trial. Based on a careful analysis of the operating characteristics of a range of futility criteria, an observed treatment effect of 0.6 point difference in KCCQ PLS (vericiguat vs placebo) was chosen to serve as the boundary for futility for both dose groups; this is approximately equivalent to a joint conditional power (CP) of 23% (under the assumption of a true difference of 5 points). An observed treatment effect <0.6 in both comparisons would therefore signal to the DMC to consider their potential recommendation that the trial should be terminated early. The type II error rate spent with this futility rule will be <0.01. Assuming the true treatment

effect is a 5 point difference as expected, the probability of stopping at the interim is approximately 1.3%. Under the null hypothesis, i.e., assuming 0 treatment effect for both vericiguat vs. placebo comparisons, the probability of stopping at the interim for futility for both doses is approximately 43%. Stopping for futility will only be done if both arms are futile. If only one arm is futile then it will not be dropped as enrollment is expected to be completed at the time of the futility analysis. At this futility boundary the trial has a probability of 9% to observe a >5 point improvement in either of the comparison in KCCQ PLS. Details of the futility analysis will be specified in the SAP and in the DMC charter. No formal interim report will be written.

Anchor-based interim analysis

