**Table 4-2: Operating characteristics for futility boundaries**

Equivalent treatment effect boundary (points)	Conditional power [1]	Joint conditional power [2]	Probability of meeting futility criterion (Observed treatment difference < boundary for both arms)		Joint probability [3] of observing a >7/5/3 point treatment effect on any dose at final analysis
			True effect = 0	True effect = 5	
1.2	20%	31%	53%	2.5%	0.004 / 0.134 / 0.696
0.7	15%	24%	44%	1.4%	0 / 0.095 / 0.621
0.6	14%	23%	43%	1.3%	0 / 0.089 / 0.605
0.5	13%	21%	40%	1.1%	0 / 0.082 / 0.590
0.4	12%	20%	38%	1.0%	0 / 0.077 / 0.574
0	10%	16%	34%	0.7%	0 / 0.056 / 0.509

[1] Probability of rejecting any individual hypothesis at the end of the study based on observed interim value (under the assumption of a true difference of 5 points).  
 [2] Joint probability of rejecting at least one of the hypotheses at the end of the study based on observed interim value (under the assumption of a true difference of 5 points).  
 [3] Joint probability of observing a treatment effect larger than certain threshold in either of the comparisons at the end of the study based on observed interim value (under the assumption of a true difference of 5 points).

An observed mean treatment effect  $<0.6$  in both comparisons (vericiguat 10 mg vs. placebo and vericiguat 15 mg vs. placebo) would therefore signal to the DSMC to consider their non-binding recommendation that the trial should be terminated early. Assuming the true treatment effect is a 5-point difference, as expected, the probability of stopping at the interim is approximately 1.3%. Under the null hypothesis, i.e., assuming 0 treatment effect for both vericiguat vs. placebo comparisons, the probability of stopping at the interim for futility is approximately 43%. If only one arm is futile then it will not be dropped as enrollment is expected to be almost completed at the time of the futility analysis. Stopping for futility will only be done if both arms meet the futility criterion. Under this observed interim value (0.6 point difference) and assuming the alternative hypothesis is true, the trial has a probability of 8.9% to observe a  $>5$  point improvement and a probability of 60.5% to observe a  $>3$  point mean improvement in either of the comparisons in KCCQ PLS at week 24. Details of the futility interim analysis will be specified in the DSMC charter. No formal interim report will be written.

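### The week-24 probabilities quoted at the 0.6-point futility boundary (joint conditional power 23%, 8.9%, 60.5%) hold only if week-12 data are treated as week-24 data, an assumption neither document states

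*SAP*

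**What the plan says.** One futility look is planned once half the patients have week-12 KCCQ data (Protocol 10.5; SAP 4.3.1). The primary endpoint is the change in PLS to week 24 (SAP 6.2.3.1).

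- **Boundary.** SAP 4.3.1 chooses an observed difference of 0.6 points from the operating characteristics in Table 4-2. It adds that "this is approximately equivalent to a joint conditional power (CP) of 23% at week 24", under a true difference of 5 points and an SD of 21. The Protocol synopsis gives the same figure: "approximately equivalent to a joint conditional power (CP) of 23" per cent.
- **What the columns mean.** Footnote 2 of Table 4-2 defines joint conditional power as "Joint probability of rejecting at least one of the hypotheses at the end of the study based on observed interim value".
- **Other week-24 chances.** At 0.6, SAP 4.3.1 says that "assuming the alternative hypothesis is true, the trial has a probability of 8.9% to observe a" benefit above 5 points, and "a probability of 60.5% to observe a" mean benefit above 3 points, at week 24. Protocol 10.5 has: "At this futility boundary the trial has a probability of 9% to observe a >5 point improvement in either of the comparison".
- **Link between the visits.** It is qualitative only: prior data suggest that "the 12 week timepoint will be sufficiently predictive of the 24 week data". Week 12 is used because "a sufficiently large proportion of data at the 24 week timepoint will only become available shortly before completion of the trial".

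Neither document gives a week-12/week-24 correlation. Both leave further detail of the futility analysis to the monitoring committee charter, which is not among the documents.

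**The concern.** Conditional power asks how likely the final test is to succeed given what has been seen. If the interim and final analyses use the same outcome, the interim patients' contribution to the final estimate is already fixed. Here it is not: a patient's week-24 score is still unknown when the week-12 score is seen. A poor week-12 difference therefore carries over to week 24 only in part, and how far depends on the correlation. Being predictive enough to justify an early look is not the same as being perfectly correlated.

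What is at stake is how the monitoring committee reads the boundary. The SAP says 0.6 was chosen from this table. A committee at the boundary that is told 23% may be looking at a trial whose chance of success, under the plan's own alternative, is clearly higher.

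**Working it through.** **Inputs.** 245 per arm and SD 21 (Protocol 10.4); two-sided alpha 0.025 per comparison (SAP 6.2.5); 50% of patients at the look, i.e. 122.5 per arm; effect 5 and SD 21 (SAP 4.3.1). The two comparisons share the placebo arm with equal allocation, so their correlation is 0.5.

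**Standard errors.**
- Final: 21 × √(2/245) = 1.897.
- Interim: 21 × √(2/122.5) = 2.683.
- Critical final difference: 2.2414 × 1.897 = 4.253.

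**Reproducing the plan's figures.** Count the observed 0.6 as half of the final estimate.
- Mean of the final difference: 0.5 × 0.6 + 0.5 × 5 = 2.8. SD: 0.5 × 2.683 = 1.342.
- Individual conditional power: P(Z > (4.253 − 2.8)/1.342 = 1.083) = 13.9% (printed 14%).
- At least one of two comparisons, correlation 0.5: joint conditional power 22.7% (printed 23%), P(>5) 0.0887 (printed 0.089), P(>3) 0.6054 (printed 0.605).

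Repeating this for all six rows matches all 24 printed values of individual conditional power, joint conditional power, P(>5) and P(>3) to rounding. In the P(>7) column the 0.6 row gives 0.0017 against a printed 0, which is immaterial.

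**General form.** Let ρ be the patient-level correlation between week 12 and week 24, d12 and SD12 the true week-12 effect and SD, and b the observed week-12 difference in both comparisons. With no week-24 data used at the look:
- mean of the final difference = 5 + 0.5 × ρ × (21/SD12) × (b − d12)
- SD of the final difference = 1.897 × √(1 − ρ²/2)

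Setting ρ = 1, d12 = 5 and SD12 = 21 returns 2.8 and 1.342, the plan's case. At ρ = 0.98 the fit already fails: joint conditional power is 24.5% and P(>5) 0.100.

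**Varying ρ, with 5 points and SD 21 at both visits.** Worked example at ρ = 0.8: mean = 5 + 0.4 × (0.6 − 5) = 3.24; SD = 1.897 × √0.68 = 1.565; z = (4.253 − 3.24)/1.565 = 0.647; individual conditional power 25.9%, joint 39.1%. The documents give no ρ, so the values below 1 are assumptions.

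| ρ | Joint CP | P(>5) | P(>3) |
|---|---|---|---|
| 1 (as printed) | 23% | 9% | 61% |
| 0.95 | 27% | 12% | 64% |
| 0.9 | 31% | 15% | 67% |
| 0.8 | 39% | 21% | 73% |
| 0.7 | 46% | 28% | 77% |

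**Varying the week-12 effect or SD, with 5 points and SD 21 still true at week 24 (assumed values, ρ = 0.9).**

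| Week-12 effect | Week-12 SD | Joint CP |
|---|---|---|
| 6 | 21 | 21% |
| 4 | 21 | 44% |
| 5 | 18 | 23% |
| 5 | 24 | 38% |

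**Stopping probabilities.** These involve only the week-12 difference, so ρ does not enter. At 0.6 they compute to 42.6% with no effect (printed 43%) and 1.24% with 5 points (printed 1.3%). Other rows differ slightly (for example, boundary 0.4 with no effect: 39.5% against 38%), which does not affect this point.

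**Power lost to the rule.** By simulation with 5 points at week 12, the chance of stopping a trial that would have rejected at least one hypothesis is 0.14% at ρ = 1, 0.43% at 0.7 and 0.62% at 0.5. All are below the 0.01 stated in Protocol 10.5.

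**The case against.** The strongest reply is that nothing is miscalculated and most of the model is disclosed. That largely stands. SAP 4.3.1 attaches one effect and one SD to the 23%, and the Table 4-2 footnotes repeat the 5-point condition. The natural reading is that 5 and 21 apply at both visits. The text also says openly that week 12 stands in for week 24, and why, and the wording is approximate. The charter may give a correlation or say how any available week-24 values are handled. What is left undisclosed is the correlation of 1. The reference to predictiveness does not supply it, and figures printed as week-24 probabilities in the SAP need it beside them.

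A second reply is that the direction is not established. This is right once the week-12 effect or SD is allowed to differ. Protocol section 5 points both ways: in the earlier phase IIb trial the week-12 difference at 10 mg exceeded 5 points, yet that arm was still rising at week 12. With a week-12 effect of 6 and correlation 0.9, joint conditional power is 21%, slightly below the printed value. A reader might infer that the true figure must exceed 23%. The documents support that only for 5 points and SD 21 at both visits.

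A third reply is that the rule is defined in points, so conditional power only describes it. That bounds the consequence, but the SAP cites this table as the basis for choosing 0.6.

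**Conclusion.** The point holds as a misstated operating characteristic. The 23%, 8.9% (9% in the Protocol) and 60.5% are the correlation-1 case, presented as the design's week-24 probabilities. Under the plan's own effect and SD at both visits, with no week-24 data used at the look, they are a lower limit. At an assumed correlation of 0.7, joint conditional power is about twice the printed figure (46% against 23%) and P(>5) about three times (28% against 9%). The documents give no correlation, so these sizes are illustrations.

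A reader might also infer that the futility rule is unsafe or that 0.6 must change. The documents do not support that: the signal is non-binding, both comparisons must fall below 0.6, and type I error is unaffected. The 43%, the 1.3% and the type II error statement also stand. The last two assume 5 points and SD 21 at week 12.

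**What to change.** 1. In Table 4-2, label the present conditional power, joint conditional power and P(>7/5/3) values as the correlation-1 case that treats week 12 as week 24.
2. Restate those columns over a stated range of week-12/week-24 correlations, or at one estimated from blinded pooled data.
3. State that 5 points and SD 21 are assumed at both visits, and whether any week-24 data enter the look. Rows for a week-12 effect above and below 5 would be useful.
4. Carry the restated figures into the Protocol synopsis, Protocol 10.5 and SAP 4.3.1.
5. Leave the 0.6 boundary, 43%, 1.3% and the type II error statement unchanged, with a note that the last two assume 5 points and SD 21 at week 12.

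If the look is still pending, the restated table should also go into the monitoring committee charter. It is probably past: SAP 4.3.2.1 already reports thresholds from the blinded analysis that was planned for when all patients had reached week 12. In that case the change belongs in the SAP and the study report. The cost is a short recalculation and some wording, with no extra patients or data and no change to the rule.

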**Table 4-2: Operating characteristics for futility boundaries**

Equivalent treatment effect boundary (points)	Conditional power [1]	Joint conditional power [2]	Probability of meeting futility criterion (Observed treatment difference < boundary for both arms)		Joint probability [3] of observing a >7/5/3 point treatment effect on any dose at final analysis
			True effect = 0	True effect = 5	
1.2	20%	31%	53%	2.5%	0.004 / 0.134 / 0.696
0.7	15%	24%	44%	1.4%	0 / 0.095 / 0.621
0.6	14%	23%	43%	1.3%	0 / 0.089 / 0.605
0.5	13%	21%	40%	1.1%	0 / 0.082 / 0.590
0.4	12%	20%	38%	1.0%	0 / 0.077 / 0.574
0	10%	16%	34%	0.7%	0 / 0.056 / 0.509

[1] Probability of rejecting any individual hypothesis at the end of the study based on observed interim value (under the assumption of a true difference of 5 points).  
 [2] Joint probability of rejecting at least one of the hypotheses at the end of the study based on observed interim value (under the assumption of a true difference of 5 points).  
 [3] Joint probability of observing a treatment effect larger than certain threshold in either of the comparisons at the end of the study based on observed interim value (under the assumption of a true difference of 5 points).

An observed mean treatment effect  $<0.6$  in both comparisons (vericiguat 10 mg vs. placebo and vericiguat 15 mg vs. placebo) would therefore signal to the DSMC to consider their non-binding recommendation that the trial should be terminated early. Assuming the true treatment effect is a 5-point difference, as expected, the probability of stopping at the interim is approximately 1.3%. Under the null hypothesis, i.e., assuming 0 treatment effect for both vericiguat vs. placebo comparisons, the probability of stopping at the interim for futility is approximately 43%. If only one arm is futile then it will not be dropped as enrollment is expected to be almost completed at the time of the futility analysis. Stopping for futility will only be done if both arms meet the futility criterion. Under this observed interim value (0.6 point difference) and assuming the alternative hypothesis is true, the trial has a probability of 8.9% to observe a  $>5$  point improvement and a probability of 60.5% to observe a  $>3$  point mean improvement in either of the comparisons in KCCQ PLS at week 24. Details of the futility interim analysis will be specified in the DSMC charter. No formal interim report will be written.

#### 4.3.2 Anchor-based analysis and responder definitions

The main analyses to aid the interpretation and definition of a responder threshold for the KCCQ PLS change scores will be based on an anchor-based approach by categorizing patients according to their responses from baseline to Visit 7 (week 12) to the Patient Global Impression of Change (PGIC) (see Section 6.2.1). A responder definition represents the threshold for meaningful within-patient change, and it can be used to categorize patients as responders or non-responders based on the KCCQ PLS scores.

Supportive anchor-based analyses will be conducted by categorizing patients according to their change in Patient Global Impression of Severity (PGIS) (see Section 6.2.1) responses from baseline to Visit 7 (week 12) (e.g. unchanged, improved by 1 response category, deteriorated by 1 response category, etc.) and additionally, change in PGIS response between week 18 and 24 (when more subjects are expected to rate themselves in the same severity category). In addition to anchor-based approaches, supportive distribution-based approaches will also be used, i.e. 0.5 standard deviation and standard error of measurement (SEM). These methods provide an indication of the smallest score that would exceed measurement error.

Graphical displays via empirical cumulative distribution function (CDF) and probability density function (PDF), receiver operating characteristics (ROC) and non-parametric discriminant analyses will also be created to support the above estimations.

These analyses will serve to support the interpretation of study results relative to thresholds for meaningful within-patient change in addition to the established thresholds of clinically meaningful between group changes for the KCCQ PLS [11,12,13]. They will be performed on blinded data, with all treatments combined, from an interim dataset prior to study unblinding. These analyses are planned for when 100% of the patients complete Visit 7 (week 12) and their KCCQ data become available. Only patients with actual data (not imputed data) on the KCCQ PLS, PGIC, PGIS at baseline and the relevant post-baseline date (collected on the same day) will be included. The blinded analysis results will be reviewed by the PRO sub-committee which will propose an appropriate responder definition estimate for within-patient

improvement and/or worsening in KCCQ PLS scores. Correlations between KCCQ-PLS and anchors will be calculated to assess the level of confidence in the interpretation of results. Correlations  $>0.35$  are generally considered acceptable, and confidence in an individual analysis is increased between KCCQ-PLS and the anchor if the correlation is moderate to strong (0.4 – 0.6) [11].

